6.6 Subgroup analyses

The adjusted analyses of the primary and secondary outcomes will be replicated:

- According to the subgroup of HCWs by COVID-19 status at entry, i.e. separately for those who already had COVID-19 at entry vs those without COVID-19 at entry
- According to the subgroup of HCWs for which PCR-confirmed absence of infection at index date is demonstrated
- According to the subgroup of HCWs for which serology results are available at entry and follow-up
- According to the time from index date to entry in the registry date. Depending on the distribution of the length of time from index date to study enrollment date in these two times, a subgroup analysis may be undertaken. Groups will be formed by binning time from index date to study enrollment date (eg. 0-1 month, 1-2 months, 2-3 months, greater than 3 months)

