3.1 Study design

The UNITY Global Registry is designed to collect data on healthcare workers exposed to SARS-CoV-2 using longitudinal serial surveys implemented through a web/mobile application-based technology to encourage participation and facilitate rapid responses during this pandemic. Countries and healthcare facilities were selected based on the availability of potential prophylactic treatments to prevent workplace infection from SARS-CoV-2. Individuals with workplace exposure to confirmed or clinically diagnosed COVID-19 patients prior to enrollment, or anticipated within 30 days after enrollment, are eligible to participate. COVID-19 exposure is defined as per WHO classification¹. The date of the HCW's first known exposure to a confirmed or clinically diagnosed case of COVID-19 is referred to as the "Index Date" (see Figure 1). Healthcare worker volunteers are ineligible if they had COVID-19 or symptoms highly suggestive of COVID-19 before the Index Date. However, at the time of enrollment, HCWs can be either SARS-CoV-2 positive (symptomatic or asymptomatic) or SARS-CoV-2 negative. Healthcare workers are identified for participation via a central contact at participating healthcare facilities and are directed to a website/mobile application allowing them to electronically consent and answer questions that help assess their eligibility to participate. Information on potential prophylactic treatments used by HCWs are also collected.

All eligible HCWs in the study facilities are asked to enter the data in the registry via electronic data collection form. Data is collected at entry to the registry, and then weekly until 12 weeks after enrollment, death or lost to follow-up, whichever is earlier. A secondary contact is identified to be contacted to confirm status of HCWs in case of non-response/ loss to follow-up. In case of conflicts, responses by HCWs take precedence. Serology results from the laboratory will be loaded into the Local Data Store and merged with HCW contact information based on the participant identification numbers. Notification of results may be made available to the HCWs via secure access.

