3.1.1.2 Exclusion criteria

- A confirmed SARS-CoV-2 infection or clinically diagnosed COVID-19 prior to the first known exposure to confirmed or clinically diagnosed COVID-19 patient (Index Date).
- Participation in a ‘blinded’ clinical trial, i.e. unaware of exact treatment received as part of the clinical trial.

Date checks to confirm eligibility criteria will be completed for all subjects. Subsequently, healthcare workers that indicate first exposure to COVID-19 infected patients or COVID-19 symptoms/diagnosis/test results prior to 2020 will be dropped from any analysis. Similarly, healthcare workers that are not exposed to COVID-19 infected patients within 30 days following enrolment will be excluded from any analysis.

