3.5 Study outcomes

3.5.1 Primary Outcome

- Occurrence of SARS-CoV-2 infection among HCWs caring for COVID-19 patients, in terms of time, geography, healthcare setting, and type of HCW. SARS-CoV-2 infection will be defined as a composite outcome diagnosed via the following methods:
 - By test – positive test results – confirmed diagnosis
 - Clinical diagnosis
 - By symptoms
 - Hospitalisation due to COVID-19 illness

Sensitivity analyses will be conducted using confirmed (by positive test results) diagnosis only, and diagnosis by other means, as specified above.

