6.4 Primary analysis

6.4.1 Frailty model: mixed effect Cox regression

For the time to COVID-19 infection outcome, both crude and adjusted hazards ratios will be estimated for time to COVID-19 infection with respect to prophylaxis use. The primary objective of this analysis is to assess the association between prophylactic treatments and the reduced risk of SARS-CoV-2 infection in HCWs caring for COVID-19 patients. A mixed effect Cox regression model (ie. frailty model) will be used to estimate adjusted hazard ratios. This method will allow the utilization of both the repeated measures gathered from each HCWs surveys, as well as the incorporation of time-varying covariates of interest such as PPE usage and COVID-19 exposure. Each subject will be included as a random effect. Both time-fixed and time-varying covariates will be included in the model. Covariates will be assessed using a univariate model, any covariates with a p-value less than 0.20 will be included in a multivariate model. A backward stepwise process will then be completed, where the covariates with largest p-value are removed one at a time until all covariates that remain are significant at the 0.10 level. The time-fixed covariates, healthcare facility and country will be included in the model regardless of their significance level. Including the healthcare facility and country covariates will make each healthcare worker's COVID-19 outcome conditionally independent on the background COVID-19 incidence occurring within each subject's healthcare facility and country. A list of additional covariates to be considered can be found in Table 5.4.1. For each subject in the control group, the index date (ie. time of first known exposure to COVID-19 patients) will be used as time zero. For HCWs that are treated with prophylaxis at any time their index date will be 7 days after initiation of treatment. Having an index date near treatment initiation will prevent the introduction of survivorship bias into the analysis.

Table 5.4.1 Model Covariates

Time-fixed/Time-varying Covariate	Covariate Name
Time-fixed Covariates	Healthcare facility, Country, Age, Biological Gender, BMI, Smoking status, Ethnicity, Blood type, Primary work location, Type of healthcare worker, Medical history

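### The SAP repeats the time-to-infection Cox model in healthcare workers who already had COVID-19 at entry, a stratum whose hazard ratio says essentially nothing about infection risk

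*SAP*

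**What the plan says.** SAP 6.6 states: "The adjusted analyses of the primary and secondary outcomes will be replicated". Its first bullet does this by COVID-19 status at entry, "separately for those who already had COVID-19 at entry vs those without COVID-19 at entry". The primary outcome is not exempted.

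The analysis being repeated is in SAP 6.4.1, where "both crude and adjusted hazards ratios will be estimated for time to COVID-19 infection with respect to prophylaxis use". In SAP 3.5.1, "SARS-CoV-2 infection will be defined as a composite outcome diagnosed via the following methods": positive test, clinical diagnosis, symptoms, or hospitalisation for COVID-19.

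Three further provisions decide who is in the stratum and how their time is counted:

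- SAP 3.1 allows infection at entry: "at the time of enrollment, HCWs can be either SARS-CoV-2 positive (symptomatic or asymptomatic) or SARS-CoV-2 negative".
- SAP 3.1.1.2 excludes earlier infection only if it came before the index date (first known exposure). Infections between index date and enrolment stay in.
- SAP 6.4.1 sets time zero. For controls, "the index date (ie. time of first known exposure to COVID-19 patients) will be used as time zero". For the treated: "For HCWs that are treated with prophylaxis at any time their index date will be 7 days after initiation of treatment".

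SAP 6.3.5 gives this subgroup one explicit job: to examine whether cardiovascular disease and stroke history can be placed before or after COVID-19. Protocol 8.7.6 does not list the subgroup.

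**The concern.** The stratum is defined by the outcome. Its members were infected between index date and entry, so each already meets the event definition, and infection times are truncated at entry. No one who escaped infection is left for comparison, so a Cox model can contrast only early with late infection among the infected. If pre-entry infections were instead not counted, nobody in the stratum would be at risk of a first infection, and the SAP defines no second one.

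The registry is meant to inform policy on prophylaxis. If an adjusted HR from this stratum is reported beside the HR from HCWs without COVID-19 at entry, readers may take the difference as effect modification by entry status. It would in fact be a product of how the stratum was selected.

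**Working it through.** **Inputs from the documents.** N = 10,000, 20% unexposed, 10% control risk in the study period, RR 0.78, 80% power (SAP 5); two-sided 5% level (SAP 6.1); 12 weeks of follow-up from enrolment (SAP 3.4). The documents give neither the gap from index date to entry nor the timing of prophylaxis initiation. Both are assumptions below.

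**The plan's own figure.** Expected events are 2,000 × 0.10 + 8,000 × 0.078 = 824. The Schoenfeld formula gives z = √(824 × 0.2 × 0.8) × |ln 0.78| − 1.96 = 11.48 × 0.2485 − 1.96 = 0.89, a power of 81.4%. This matches the stated 80%. The point does not depend on it, but it fixes the 80:20 split and the 10% risk.

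**Why the HR sits near 1 with a common clock.** Take constant hazards and a fixed gap. Let S be the probability of being uninfected at entry. Among those infected by entry, the share infected in the first half of the gap is (1 − √S)/(1 − S) = 1/(1 + √S).

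- Controls, 10% risk: S = 0.90, share = 1/(1 + 0.9487) = 51.3%.
- Treated, true HR 0.78: S = 0.90^0.78 = 0.9211, share = 1/(1 + 0.9597) = 51.0%.
- Treated, true HR 0.5: S = 0.90^0.5 = 0.9487, share = 1/(1 + 0.9740) = 50.7%.

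A true HR of 0.5 cuts the risk from 10.0% to 5.1%, but moves the timing among the infected by less than one percentage point. The stratum sees only the timing.

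**Simulation, common time zero.** 10,000 HCWs, 80% treated, constant hazards, 12-week gap, 200 replicates, Cox fit in those infected by entry:

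| Control risk before entry | True HR 1.00 | True HR 0.78 | True HR 0.50 |
|---|---|---|---|
| 5% | 0.989 | 1.014 | 0.986 |
| 10% | 1.002 | 0.985 | 0.993 |
| 20% | 0.999 | 0.985 | 0.976 |
| 40% | 1.001 | 0.970 | 0.937 |

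At 10% risk the SD of the log HR is 0.08 to 0.09 in a single study, far larger than any difference across that row. Varying the gap (84 days fixed, or up to 90 or 180 days) at 10% risk per 12 weeks gives about 0.97 to 1.00 for all three true HRs.

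**Simulation, SAP time zeros.** Same stratum, 10% risk per 84 days, the same three gaps and three true HRs, infections before time zero dropped. The result follows the assumed start of prophylaxis:

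- start spread evenly between index date and entry: about 1.6 to 2.5;
- start within 14 days after the index date: about 1.0 to 1.7;
- start up to 60 days before the index date: about 0.35 to 0.60.

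Within each combination of start and gap, the HR barely moves with the true effect. With a fixed 12-week gap and evenly spread starts, it is 2.36, 2.33 and 2.31 for true HRs of 1.00, 0.78 and 0.50.

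**The other stratum.** In HCWs without COVID-19 at entry, with the 12-week gap, 10% risk, a common time zero and delayed entry at enrolment, the Cox HR recovers the truth: 0.995, 0.778 and 0.495. With the SAP's time zeros and no delayed entry, single runs across the same assumptions gave 0.69 to 1.74 for a true HR of 1.0, and 0.52 to 1.63 for a true HR of 0.78.

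**The case against.** Several points can be made for the plan.

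- **The subgroup has a stated purpose.** SAP 6.3.5 uses it to look at the dating of medical history. That stands, and the cross-reference must be amended if the stratum goes. It does not require an infection HR among the already infected.
- **SAP 6.6 also covers secondary outcomes.** For hospitalisation, severe disease and death, HCWs infected at entry can be informative about progression. That stands, and it limits the point to the primary outcome.
- **Protocol 8.7.4 mentions repeated time-to-event analyses,** under which infected HCWs might be at risk again. The SAP defines no reinfection event, so this does not rescue the analysis as written.
- **The consequence is limited.** This is one exploratory subgroup bullet. It leaves the primary estimate untouched, and the shell tables contain no subgroup HR. That stands.

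A reader might also infer three stronger things that the documents do not support:

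- **That the stratum will always suggest no effect or harm.** SAP 6.3 and 6.3.7 expect prophylaxis both before and after first exposure. Starts before the index date push the HR well below 1, which would look like strong benefit. This distortion in either direction comes from the unequal time zeros in SAP 6.4.1, which affect the whole primary analysis, and should not be counted as the size of this point.
- **That the stratum without COVID-19 at entry is sound as it stands.** The SAP states no delayed entry, so time from index date to enrolment, event-free by selection, would count as time at risk.
- **That the HR carries no information at all.** A small residual appears when cumulative risk before entry is high: about 0.94 at 40% risk with a true HR of 0.5.

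**Conclusion.** The point holds for the primary outcome, and SAP 6.6 is wrong as written there. The time-to-infection HR in HCWs already infected at entry cannot answer the question put to it. With a common time zero and 10% risk per 12 weeks, a true HR of 0.5 and a true HR of 1.0 give practically the same result. This rests on constant hazards, an 80:20 split and the assumed gaps from index date to entry. The main conclusion does not hang on those figures: selecting on the event removes the comparison between infected and uninfected whatever the gap. The point does not extend to severity outcomes among the infected, nor does it by itself call the primary estimate into question.

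**What to change.** 1. In SAP 6.6, for the primary outcome, drop the stratum that already had COVID-19 at entry. Report only HCWs without COVID-19 at entry, and state that their time at risk starts at enrolment (delayed entry), or at time zero where that falls later.
2. Keep the infected-at-entry group for the description of prophylaxis before infection in SAP 6.3.7 and for severity outcomes (hospitalisation, severe disease, death), labelled as progression among the infected.
3. In SAP 6.3.5, amend the cross-reference so that the medical-history dating question is addressed by comparing the full-cohort result with the result in HCWs uninfected at entry.

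The unequal time zeros in SAP 6.4.1 need their own correction; this change does not repair them.

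The cost is an edit to one bullet, one added sentence on delayed entry and one amended cross-reference. No protocol commitment is broken, since protocol 8.7.6 does not list this subgroup. What is lost is one exploratory HR with essentially no information on infection risk.

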Enrollment will be monitored and potentially capped to ensure that the study enrolls an aggregate of at least 75% of HCWs who are taking a potential prophylactic therapy.

For details on the information collected and the overall study design, refer to [Table 1](#), [Table 2](#), [Figure 1](#), and [Figure 2](#), respectively.

This is a comparative observational cohort study; therefore, no preventive interventions, visits or laboratory tests are mandated. Dosing and duration of potential prophylactic treatment is at the discretion of the institution and/or healthcare provider, in accordance with regular local practice. However, serology testing for SARS-CoV-2 antibodies may be offered to approximately 50% of participating HCWs per country, at enrollment (ranging from baseline up to Week 4 [African countries] and Week 8 [Pakistan]) and at the last follow-up (i.e. at Week 12).

Figure 1 Study Schematic - High-level

HCW: Healthcare Worker

Figure 2 Study Schematic – Healthcare Worker Flow

[figure not shown]

Table 1 Schedule of Assessments – Healthcare Worker Flow

Variable domain	At Enrollment		Weekly follow-up (until Week 12) ^c	
	HCW	HCW	Secondary Contact	
Inclusion/eligibility criteria (screening questions/index date)	X	-	-	-
Electronic/paper (if applicable) consent	X	-	-	-
Demographics	X	-	-	-
Underlying conditions	X	-	-	-
Job characteristics	X	-	-	-
BCG vaccination history	X	-	-	-
Household history (COVID-19)	X	X	-	-
COVID-19 exposure	X	X	-	-
Prophylactic treatments	X	X	-	-
Concomitant medications	X	X	-	-
COVID-19 vaccination ^e	X	X	-	-
PPE	X	X	-	-
COVID-19 symptoms	X	X	-	-
SARS-CoV-2 testing	X	X	-	-
Serology testing ^f	X	X ^b	-	-
WHO Ordinal Scale for Clinical Improvement ^d	X	X	-	X ^a

BCG: Bacillus Calmette–Guérin; CoV: Coronavirus; HCW: Healthcare worker; PPE: Personal Protective Equipment; SARS: Severe acute respiratory syndrome; WHO: World Health Organization.

^a: In case HCWs stop responding (after due diligence reminders), their secondary contacts will be approached. In case of conflicts, responses by HCWs will be considered.

^b: Testing to be requested at last (Week 12) follow-up.

^c: Or, time since last follow-up, whichever is greater.

^d: Adapted, abbreviated version.

^e: From the time the questions on vaccination go live in the web application online survey, baseline vaccination information will only be collected for newly enrolled HCW and for HCWs who did not complete the survey prior to the addition of vaccination questions.

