^f: As a result of the COVID-19 pandemic, the production of serology kits, and shipments to various countries were delayed. It will therefore be allowed for the baseline sample to be collected from the following timepoints (ranging from baseline up to Week 8).

Table 2 Schedule of Assessments – Facility-Level

Variable domain	Prior to study	End of study
Country, region	X	-
Urban or rural setting	X	-
Type of facility (public/private/community healthcare)	X	-
Teaching/university hospital or non-teaching	X	-
Capacity		
number of patients tested for COVID-19	X	X
number of COVID-19 patients treated	X	X
number of hospital beds (overall, ICU, emergency department)	X	X
number of exposed HCWs	X	X
number of HCWs tested for COVID-19	X	X
Number of HCWs who developed confirmed or clinically diagnosed COVID-19	X	X
Number of HCWs who died from COVID-19	X	X
Approved PPE use policy, and experience of PPE shortage	X	X
Approved prophylactic treatment policy	X	X
Shortage of COVID-19 related tests	X	X
BCG vaccination policy	X	X

HCW: Healthcare worker; PPE: Personal Protective Equipment; BCG: Bacillus Calmette–Guérin.

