This is an observational cohort study; therefore, no preventive interventions, visits or laboratory tests are mandated. Dosing and duration of potential prophylactic treatment is at the discretion of the institution and/or healthcare provider, in accordance with regular local practice. However, serology testing for SARS-CoV-2 antibodies are being offered to the first 50% of participating HCWs per country, at enrollment and at the last follow-up (i.e. at Week 12).

Figure 1: Healthcare Worker Flow – Study Schematic

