7.6 Protopathic bias

- The study may also be affected by protopathic bias in which the timing of, for example, formal diagnosis with regard to when symptoms and treatment occurs can result in incorrect causal inference regarding the effect of the treatment exposure on the risk of the outcome. To assess the impact of this bias, as outlined in section 5.6, sensitivity analyses will be conducted among the subgroup of HCWs for which PCR-confirmed absence of infection at index date is demonstrated, and according to the subgroup of HCWs for which serology results are available.

8 References

1. COVID-19 Therapeutic Trial Synopsis. https://www.who.int/blueprint/prioritydiseases/key-action/COVID19_Treatment_Trial_Design_Master_ProtocolSynopsis_Final_18022020.pdf?ua=1. Last accessed on 23Apr 2020.
2. Risk assessment and management of exposure of health care workers in the context of COVID-19. WHO Interim Guidance, 19 Mar 2020. https://apps.who.int/iris/bitstream/handle/10665/331496/WHO-2019-nCovHCW_risk_assessment-2020.2-eng.pdf. Last accessed on 14 Apr 2020.
3. Austin, Peter. (2017). A Tutorial on Multilevel Survival Analysis: Methods, Models and Applications: Multilevel Survival Analysis. International Statistical Review. 85. 10.1111/insr.12214.
4. Grafféo, Nathalie & Latouche, Aurélien & Le Tourneau, Christophe & Chevret, Sylvie. (2019). ipcwswitch: An R package for inverse probability of censoring weighting with an application to switches in clinical trials. Computers in Biology and Medicine. 111. 103339. 10.1016/j.combiomed.2019.103339.

9 Appendix

WHO Ordinal Scale for Clinical Improvement¹

Patient State	Descriptor	Score
Uninfected	No clinical or virological evidence of infection	0
Ambulatory	No limitation of activities	1
	Limitation of activities	2
Hospitalized Mild disease	Hospitalized, no oxygen therapy	3
	Oxygen by mask or nasal prongs	4
Hospitalized Severe Disease	Non-invasive ventilation or high-flow oxygen	5
	Intubation and mechanical ventilation	6
	Ventilation + additional organ support – pressors, RRT, ECMO	7
Dead	Death	8

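### The serology subgroup offered as a check on protopathic bias selects HCWs for having results rather than for a negative first result, and has no rule for late entry samples

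*SAP*

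**What the plan says.** **Who is selected.** SAP 6.6 repeats the adjusted analyses of the primary and secondary outcomes in "the subgroup of HCWs for which serology results are available at entry and follow-up". It sets no condition on the result. The bullet just above does set one: "According to the subgroup of HCWs for which PCR-confirmed absence of infection at index date is demonstrated".

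**What the subgroup is for.** To assess protopathic bias, SAP 7.6 names the PCR-negative subgroup and then an analysis "according to the subgroup of HCWs for which serology results are available". Protocol 8.9 makes the same offer, and Protocol 8.7.6 lists both subgroups as sensitivity analyses.

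**Who can be in the registry.** Under Protocol 8.1 and SAP 3.1 an HCW may be SARS-CoV-2 positive or negative at enrollment.

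**When the samples are taken.** SAP 3.1 says "serology testing for SARS-CoV-2 antibodies are being offered to the first 50% of participating HCWs per country, at enrollment and at the last follow-up", the last follow-up being Week 12. SAP section 1 states that the plan is based on protocol version 1.0. Protocol v1.1 section 8.1 now allows the enrollment sample over a period "ranging from baseline up to Week 4 [African countries] and Week 8 [Pakistan". Table 1 footnote f allows the "baseline sample to be collected from the following timepoints (ranging from baseline up to Week 8", with no split by country. Protocol 8.2 also lists Indonesia, for which the text of 8.1 gives no window.

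**The concern.** Protopathic bias arises here if an HCW starts a drug because of early symptoms, or while an infection is unrecognised, and the infection is then counted against treated time. A subgroup guards against this only if its members can be shown to be uninfected when their time at risk begins. Having a serology result does not show that; a negative one helps to.

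Two further features weaken the check. Asking for results at both entry and follow-up tilts the subgroup towards HCWs still responding at Week 12, although Protocol 8.9 itself warns of loss to follow-up that differs by COVID-19 status. And once the entry sample may be drawn weeks after entry, a positive can reflect infection before or after enrollment. SAP 3.5.1 counts positive tests in the primary outcome without limiting them to PCR, and SAP 3.6.5 lists serology as a test type, so a late positive could be read either as prevalent infection or as an event.

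At stake is whether agreement between this subgroup and the main result could be taken as reassurance about protopathic bias.

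**Working it through.** **1. What the rule admits.**

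| HCW | PCR subgroup | Serology subgroup as written |
|---|---|---|
| Shown negative | in | in, if both samples exist |
| Shown positive | out | in, if both samples exist |
| Negative first sample, lost before Week 12 | not affected | out, unless another follow-up serology result was recorded |

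The second row is the defect: HCWs with evidence of earlier infection are not removed.

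**2. What a late first sample can show.** A negative at Week 4 or 8 supports no infection at entry, unless antibodies faded or never formed. A positive at Week 4 or 8 cannot be placed before or after entry.

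**3. How much infection could precede a late sample.** Inputs: 10% risk in the unexposed, 20% unexposed and relative risk 0.78 (Protocol 8.7.7, SAP 5); 12 weeks of follow-up (SAP 3.4).

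The plan's power figure is consistent with these inputs. Expected events are 2,000 × 0.10 + 8,000 × 0.078 = 824. The Schoenfeld formula gives √(824 × 0.2 × 0.8) × |ln 0.78| − 1.96 ≈ 0.89, a power of 81.4% against the stated 80%. The point made here does not rest on that figure.

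The plan gives the 10% for the study period. Reading it as a 12-week risk at constant hazard is an assumption. The cumulative risk by week w is then 1 − (1 − r)^(w/12).

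| | Week 4 | Week 8 |
|---|---|---|
| Unexposed, r = 0.10 | 1 − 0.9^(4/12) = 3.45% | 1 − 0.9^(8/12) = 6.78% |
| Share of 12-week infections | 3.45/10 = 34.5% | 6.78/10 = 67.8% |
| Exposed, r = 0.078 | 2.67% | 5.27% |
| Share of 12-week infections | 34.2% | 67.6% |

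These shares are close to 4/12 and 8/12. They are upper bounds: every draw is placed at the end of its window and no seroconversion lag is allowed. If 5,000 HCWs (about 50% of 10,000) had serology, 5,000 × (0.2 × 0.10 + 0.8 × 0.078) = 412 infections would be expected. About 141 of them could precede a Week 4 draw, or 279 a Week 8 draw, if all draws were that late.

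**4. How ambiguous a late positive is.** This depends on seroprevalence at entry, π, which the documents do not give. With pooled 12-week risk 0.2 × 0.10 + 0.8 × 0.078 = 0.0824, the post-entry infections by week w are i = (1 − π)(1 − 0.9176^(w/12)), and their share of positives is i/(i + π).

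| Assumed π | Week 4 | Week 8 | Week 4, assumed 2-week lag | Week 8, assumed 2-week lag |
|---|---|---|---|---|
| 5% | 34.9% | 51.4% | 21.3% | 44.4% |
| 10% | 20.3% | 33.4% | 11.4% | 27.5% |
| 20% | 10.2% | 18.2% | 5.4% | 14.4% |
| 30% | 6.2% | 11.5% | 3.2% | 8.9% |

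The ambiguity ranges from slight to about half of late positives.

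**The case against.** **Other checks exist.** SAP 7.6 names the PCR-negative subgroup first, and SAP 6.6 also splits by COVID-19 status at entry. SAP 6.4.1 starts treated HCWs' time 7 days after initiation; the stated reason is survivorship bias, but if earlier diagnoses are excluded this would also lessen protopathic bias. This stands: a reader might infer that protopathic bias goes unexamined, and the documents do not support that. But no laboratory tests are mandated, so a PCR result at the index date depends on incidental testing, and clinical status at entry is self-reported. Serology is the check that could reveal unrecognised earlier infection.

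**Late sampling does not make the sample useless.** A reader might infer that a Week 4 or 8 sample cannot show absence of infection at entry. That goes too far, because a late negative still supports absence. It does not rescue the rule as written, which does not select on negatives.

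**Paired results carry information.** Two samples can separate seroconversion from earlier infection. True, but SAP 6.6 and 7.6 do not say how the results are to be used.

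**Completion to Week 12 is not strictly required.** SAP 6.6 says only follow-up, and Protocol Appendix 2 also records serology as a test type at weekly follow-up. The fair statement is that the rule favours retained HCWs, since Week 12 is when the protocol offers the second sample.

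**The stakes are limited.** Serology is optional, and the amendment rationale says that it is not part of the endpoints or objectives. The primary estimate does not depend on this subgroup. The protocol and SAP nevertheless offer it as evidence on bias.

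**Conclusion.** The point holds. Followed exactly, the rule keeps previously infected HCWs in a subgroup meant to help assess protopathic bias, so that subgroup cannot do its job. This is a stated rule that fails its purpose, not a missing detail, and it follows from the text without any calculation.

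The timing problem is secondary. The SAP has not taken up the v1.1 sampling window, and late positives cannot be dated. The 34.5% and 67.8% bound how much follow-up infection could precede the sample. They rest on a 12-week reading of the 10% risk, a constant hazard, no seroconversion lag and draws at the outer limit. They are not expected values and say nothing about the size of any bias in the hazard ratio. The defect is worth correcting in a supporting analysis; it does not undermine the primary analysis.

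**What to change.** In SAP 6.6 and 7.6:

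- Define the subgroup as HCWs seronegative on their first sample, and state the draw window.
- Start time at risk at the draw date. Otherwise a negative late sample guarantees infection-free time before it (immortal time).
- Keep prophylaxis as the exposure defined in the main analysis, updated over time from the draw. Freezing it at the draw would conflict with the dynamic exposure in Protocol 8.7.4 and misclassify later starters.
- Do not require a Week 12 sample.
- Exclude HCWs positive on a late first sample from this subgroup and report their number.

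Align the SAP with protocol v1.1, and reconcile Protocol 8.1 with Table 1 footnote f, including the position of Indonesia. Protocol 8.7.6 uses the same availability wording, so the change should be recorded as a deviation, as Protocol 8.7 provides.

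The cost is mainly SAP wording, plus a smaller subgroup with shorter follow-up and fewer events. Under the assumptions above, a Week 4 draw leaves 12 − 4 = 8 weeks and 100 − 34.5 = 65.5% of 12-week infections; a Week 8 draw leaves 4 weeks and 100 − 67.8 = 32.2%. Dropping the Week 12 requirement also means that infections detectable only by seroconversion may be missed in HCWs without a second sample.
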